5.3. Treatment Regimens

All eligible subjects will be treated with pomalidomide and dexamethasone.

5.3.1. Phase 1

Ibrutinib in combination with pomalidomide and dexamethasone will be administered according to the assigned cohort.

5.3.2. Randomized Phase 2b (Treatment Arms A and B)

During the conduct of the randomized study portion, subjects will be randomly assigned to treatment with either ibrutinib in combination with pomalidomide and dexamethasone (Arm A) or matching placebo in combination with pomalidomide and dexamethasone (Arm B). The final dose level for conducting the Phase 2b portion will be determined by the Phase 1 MTD/MAD.

Each cycle is 28-days in length. Missed doses of ibrutinib and pomalidomide will not be made up. During the conduct of the Phase 2b study portion, dose escalation of any agent (ibrutinib or

placebo, pomalidomide or dexamethasone) at any time will not be allowed. Treatment will continue until IRC confirmed disease progression or other reason for treatment discontinuation as outlined in [Section 5.8](#).

5.3.2.1. Treatment Arm A

Ibrutinib: Phase 2b dose orally administered daily

Pomalidomide: 4 mg orally administered Days 1-21 of each 28-day cycle

Dexamethasone: Age-adjusted dose orally administered weekly on Days 1, 8, 15 and 22 of each 28-day cycle

5.3.2.2. Treatment Arm B

Placebo: Matched placebo orally administered daily

Pomalidomide: 4 mg orally administered Days 1-21 of each 28-day cycle

Dexamethasone: Age-adjusted dose orally administered weekly on Days 1, 8, 15 and 22 of each 28-day cycle

5.3.3. Open-Label Sub-Study (Treatment Arm C)

Ibrutinib: Phase 2b dose orally administered daily

Pomalidomide: 4 mg orally administered Days 1-21 of each 28-day cycle

Dexamethasone: Age-adjusted dose orally administered weekly on Days 1, 8, 15 and 22 of each 28-day cycle

All subjects treated in this sub-study will follow guidelines for ibrutinib or placebo dosing and toxicity management as described for the randomized treatment arms (Arm A and Arm B) in the protocol.

5.4. Ibrutinib or Placebo

All subjects in Phase 1 and those assigned to Treatment Arm A and Treatment Arm C in Phase 2b of this study will receive ibrutinib. All subjects assigned to Treatment Arm B in Phase 2b of this study will be administered placebo. All subjects taking ibrutinib or matching placebo will follow guidelines for ibrutinib dosing and toxicity management.

5.4.1. Formulation, Packaging, and Storage of Ibrutinib or Placebo

Ibrutinib or placebo capsules are provided as a hard gelatin capsule containing 140 mg of ibrutinib or placebo. All formulation excipients are compendial and are commonly used in oral formulations. Refer to the [ibrutinib IB](#) for a list of excipients.

The ibrutinib or placebo capsules will be packaged in opaque high-density polyethylene plastic bottles with labels bearing the appropriate label text to meet the applicable regulatory requirements. All study drug will be dispensed in child-resistant packaging.

Refer to the Pharmacy Manual for additional guidance on study drug storage, preparation and handling.

5.4.2. Dose and Administration of Ibrutinib or Placebo

The first dose of ibrutinib or placebo will be administered orally in the clinic on Cycle 1 Day 1, of the Treatment Phase, after which ibrutinib or placebo will be self-administered daily by the subjects on an outpatient basis.

Ibrutinib or placebo will be dosed at the same time as pomalidomide and dexamethasone on the days of PK assessment.

Ibrutinib or placebo is administered orally once daily with 8 ounces (approximately 240 mL) of water at approximately the same time each day. The capsules should be swallowed intact and patients should not attempt to open capsules or dissolve them in water. The use of strong CYP3A inhibitors/inducers, and grapefruit and Seville oranges should be avoided for the duration of the study ([Section 6.1.2.1](#)).

If a dose is missed, it can be taken as soon as possible on the same day with a return to the normal schedule the following day. The subject should not take extra capsules to make up the missed dose.

Ibrutinib or placebo dosing is continuous (without interruption) throughout the Treatment Phase. If Day 1 pomalidomide or dexamethasone dosing is delayed for toxicity that does not require ibrutinib or placebo to be held for toxicity, dosing of ibrutinib or placebo should continue. If a Day 1 (of any Cycle) is delayed due to scheduling delays, ibrutinib or placebo dosing should continue.

Treatment will continue until disease progression (confirmed by IRC for Phase 2b) or other reason for treatment discontinuation as outlined in [Section 5.8](#).

Dose modifications for toxicity are outlined in [Section 5.4.4](#).

Ibrutinib or placebo will be dispensed to subjects in bottles. Unused ibrutinib or placebo capsules dispensed during previous visits must be returned and drug accountability records updated at the beginning of the next cycle. Returned capsules must not be re-dispensed to anyone.

5.4.3. Dose Hold, Reduction or Discontinuation of Ibrutinib or Placebo

In order to continue ibrutinib or placebo at the start of a new cycle, the subject must not meet any of the criteria for ibrutinib or placebo dose modification (see [Section 5.4.4](#)).

Treatment with ibrutinib or placebo should be withheld for any unmanageable, potentially study drug-related non-hematological toxicity that is Grade 3 or higher in severity and any hematologic toxicity meeting the criteria in Section 5.4.4. Subjects who require full-dose of anticoagulant treatment (eg, warfarin or heparin) should have ibrutinib or placebo held until stable on anticoagulant therapy (Section 6.1.2.4). Subjects that require an invasive procedure or surgery must have ibrutinib or placebo withheld according to the guidance in Section 6.2. Any other clinically important events where dose delays may be considered appropriate by the Investigator should be discussed with the Medical Monitor.

Ibrutinib or placebo may be withheld for a maximum of 28 consecutive days for toxicity. Ibrutinib or placebo should be discontinued in the event of an ibrutinib or placebo toxicity lasting more than 28 days, unless reviewed and approved by the Medical Monitor.

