5.4.4. Dose Modification of Ibrutinib or Placebo

The dose of ibrutinib or placebo should be modified according to the dose modification guidelines in Table 4 if any of the following toxicities occur:

- Grade 4 neutropenia (ANC <500/ μ L) for more than 7 days. Refer to Section 6 for instruction regarding the use of growth factor support
- Grade 3 thrombocytopenia (platelets <50,000/ μ L) in the presence of clinically significant bleeding events
- Grade 4 thrombocytopenia (platelets <25,000/ μ L)
- Grade 3 or 4 nausea, vomiting, or diarrhea if persistent, despite optimal anti-emetic and/or anti-diarrheal therapy
- Any other Grade 4 or unmanageable Grade 3 toxicity attributed to ibrutinib or placebo

For Grade 3 or 4 atrial fibrillation or persistent atrial fibrillation of any grade, consider the risks and benefits of ibrutinib or placebo treatment.

If clinically indicated, the use of anticoagulants or antiplatelet agents may be considered for the thromboprophylaxis of atrial fibrillation (Section 6.1.2.4).

Table 2: Ibrutinib or Placebo Dose Modification Guidance

Hematologic Adverse Events	
Occurrence	Action to be Taken
First	Withhold ibrutinib or placebo until recovery to an ANC $\geq 750 \mu\text{L}$ or platelets $> 25,000 \mu\text{L}$ with no evidence of Grade ≥ 2 bleeding; may restart at original dose level
Subsequent ^a	Withhold ibrutinib or placebo until recovery to an ANC $\geq 750 \mu\text{L}$ or platelets $> 25,000 \mu\text{L}$ with no evidence of Grade ≥ 2 bleeding; may restart at 1 dose level lower (refer to Table 3)
Non-Hematologic Adverse Events	
Occurrence	Action to be Taken
First	Withhold ibrutinib or placebo until recovery to Grade ≤ 1 or baseline; may restart at original dose level
Subsequent ^a	Withhold ibrutinib or placebo until recovery to Grade ≤ 1 or baseline; may restart at 1 dose level lower (refer to Table 3)

^a Do not dose below 280 mg daily

Table 3: Ibrutinib or Placebo Dose Modifications

Starting Dose Level	840 mg	560 mg	420 mg
Dose Reduction Level 1	700 mg	420 mg	280 mg
Dose Reduction Level 2	560 mg	280 mg	140 mg
Dose Reduction Level 3	420 mg	Discontinue	Discontinue
Dose Reduction Level 4	280 mg	NA	NA
Dose Reduction Level 5	Discontinue	NA	NA

For required dose modification for hepatic impairment refer to Section 5.4.5 and for concomitant treatment with CYP3A inhibitors refer to [Section 6.1.2.1](#).

If ibrutinib or placebo is discontinued for toxicity, subject will end the Treatment Phase of the study.

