5.5.4. Dosage, Preparation and Administration of Pomalidomide

The first dose of pomalidomide will be administered orally in the clinic on Cycle 1 Day 1, of the Treatment Phase, after which pomalidomide will be self-administered daily by the subjects on Days 1-21 of each cycle.

Pomalidomide will be dosed at the same time as ibrutinib or placebo and dexamethasone on the days of PK assessment.

Pomalidomide can be taken with or without food and administered with water at approximately the same time each day. The capsule should be swallowed intact and subjects should not attempt to chew capsules, open capsules or dissolve them in water. Females of childbearing potential (FCBP) should not handle or administer pomalidomide unless they are wearing gloves.

If a dose of pomalidomide is missed, it should be taken as soon as possible on the same day. If a dose is missed for the entire day, it should not be made up.

Pomalidomide dosing during the Treatment Phase occurs on Days 1-21 each cycle followed by a mandatory 7-day drug-free interval. If a Day 1 (of any Cycle) is delayed due to scheduling, instruct the subject that pomalidomide dosing should not be initiated until Day 1 assessments can occur.

Treatment will continue until disease progression (confirmed by IRC for Phase 2b) or other reason for treatment discontinuation as outlined in [Section 5.8](#).

Dose modifications for toxicity are outlined in [Section 5.4.5](#).

For instructions regarding drug accountability and disposal/return of unused pomalidomide refer to the Pharmacy Manual.

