5.5.5. Dose Delay, Reduction or Discontinuation of Pomalidomide

In order to initiate a new cycle of therapy with pomalidomide, the subject must have an ANC $\geq 800/\mu\text{L}$ and a platelet count $\geq 30,000/\mu\text{L}$ and no pomalidomide related \geq Grade 3 toxicity on Day 1. If these two criteria are not met, a repeat assessment is to be performed at least weekly or more frequent per the Investigator's decision. The initiation of pomalidomide should be delayed

until the subject meets the above criteria at which time the subject will initiate drug without dose modification.

If the treatment has been interrupted and the next cycle is delayed beyond 28 days after Day 1 of the prior cycle, then Day 1 of the next cycle will be defined as the first day that treatment is resumed.

Once a cycle has initiated, if pomalidomide must be held for toxicity during dosing, omitted doses should not be made up and pomalidomide will not resume until Day 1 of the subsequent cycle, provided the subject meets the cycle initiation criteria above, with dose adjustments as per Table 4.

Treatment with pomalidomide should be withheld for any potentially study drug-related non-hematological toxicity that is Grade 3 or higher in severity and any hematologic toxicity as described in Table 4. In the event the subject is diagnosed with a thyroid condition, develops a rash or renal impairment (serum creatinine >3.0), refer to Table 4 for further instructions.

Any other clinically important events where dose delays may be considered appropriate by the Investigator should be discussed with the Medical Monitor.

Pomalidomide may be withheld for a maximum of 28 consecutive days for toxicity. Pomalidomide treatment should be discontinued in the event of a pomalidomide related toxicity lasting more than 28 days, unless reviewed and approved by the Medical Monitor.

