Venous thromboembolism \geq Grade 3	
 • Interrupt pomalidomide treatment for the remainder of the cycle • Initiate therapeutic anticoagulation – see Section 6.1.2.4. • Resume pomalidomide without dose modification at the start of the next cycle if the benefit of therapy on this study outweighs the risk for bleeding.
Hypo/hyperthyroidism \geq Grade 2	
 • Interrupt pomalidomide treatment for the remainder of the cycle • Evaluate etiology and initiate appropriate therapy • Resume pomalidomide without dose modification at the start of the next cycle at the discretion of the investigator. Do not initiate a new cycle until the subject meets cycle initiation criteria (see Section 5.5.5).
Serum creatinine >3.0 mg/dL	
 • Interrupt pomalidomide treatment. • Do not initiate a new cycle or resume treatment until the serum creatinine is <3.0 mg/dL and resume without dose modification.

Toxicity	Intervention
Any other Grade 3/4 non-hematologic toxicities attributed to pomalidomide	
 • Interrupt pomalidomide treatment for the remainder of the cycle. • Reduce the dose of pomalidomide by one dose level (1 mg) at the start of the next cycle. Do not initiate a new cycle until the patient meets cycle initiation criteria (see Section 5.5.5). Do not dose below 1 mg daily.

Table 5: Dose Reduction of Pomalidomide

Starting Dose Level	4 mg
Dose Reduction 1	3 mg
Dose Reduction 2	2 mg
Dose Reduction 3	1 mg
Dose Reduction 4	Discontinue

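### The ibrutinib hold sentence in Protocol 5.4.3 omits manageable mid-cycle Grade 4 non-hematologic events that 5.4.4 withholds for, and two dose-modification pointers lead to the other drug's rules

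*Protocol*

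**What the plan says.** **Ibrutinib or placebo.** Protocol 5.4.3 opens with a rule for starting a new cycle: the subject may continue only if none of the 5.4.4 modification criteria is met. It then gives the hold instruction: "Treatment with ibrutinib or placebo should be withheld for any unmanageable, potentially study drug-related non-hematological toxicity that is Grade 3 or higher in severity". The same sentence goes on to hold for hematologic toxicity by reference to 5.4.4.

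Section 5.4.4 lists five triggers: three hematologic, one for nausea, vomiting or diarrhea that persists despite optimal treatment, and a residual one, "Any other Grade 4 or unmanageable Grade 3 toxicity attributed to ibrutinib or placebo". Atrial fibrillation has its own risk-benefit sentence. Table 2 gives the action. For non-hematologic events, ibrutinib is withheld until recovery to Grade 1 or baseline. It may restart at the original dose after the first occurrence and one level lower after later ones.

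**Pointers.** The opening sentence of 5.4.4 reads: "The dose of ibrutinib or placebo should be modified according to the dose modification guidelines in Table 4". Table 4 is the pomalidomide toxicity table in 5.5.6; Table 2 is the one titled for ibrutinib or placebo. Section 5.5.4, on pomalidomide, refers the reader to 5.4.5 for toxicity modifications. Section 5.4.5 covers ibrutinib or placebo dosing in subjects who develop hepatic impairment and does not mention pomalidomide.

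**The concern.** These are operative safety instructions. In 5.4.3 the word for unmanageable governs everything at Grade 3 or higher. In the 5.4.4 residual trigger it governs Grade 3 only. The two sections therefore set different thresholds for the same action, and the sentence a site is likely to consult when deciding on a hold is the narrower one. A site that kept dosing through a manageable Grade 4 event on the strength of 5.4.3 would deviate from 5.4.4 because of the wording.

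The 5.4.4 pointer adds to this. Sections 5.4.2, 5.4.3 and 5.4.5 all direct the reader to 5.4.4, and its first sentence then names the wrong table. Followed literally, it gives a different dosing rule.

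**Working it through.** No figure in the plan is at issue, so the check compares the rules case by case and traces each pointer to its target.

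**Step 1: the ibrutinib hold, mid-cycle.** Take a non-hematologic event attributed to ibrutinib or placebo, so that it meets the attribution wording of both sections. Leave out nausea, vomiting, diarrhea and atrial fibrillation, which 5.4.4 handles separately.

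| Event | 5.4.3 hold sentence | 5.4.4 residual trigger with Table 2 |
|---|---|---|
| Grade 3, manageable | no hold | no hold |
| Grade 3, unmanageable | hold | hold |
| Grade 4, manageable | not covered | hold |
| Grade 4, unmanageable | hold | hold |

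The sections differ in 1 of 4 combinations. Within 5.4.4 this concerns 1 of 5 triggers (3 hematologic + 1 gastrointestinal + 1 residual = 5).

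**Step 2: the same event at the start of a cycle.** The first sentence of 5.4.3 applies every 5.4.4 criterion, so the third row also leads to a hold. The gap exists only between cycle starts.

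**Step 3: the pointers.**

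| Where | Drug | Points to | Content of target | Correct target |
|---|---|---|---|---|
| 5.4.4 | ibrutinib or placebo | Table 4 | pomalidomide | Table 2 |
| 5.5.4 | pomalidomide | 5.4.5 | ibrutinib in hepatic impairment | 5.5.5 and 5.5.6 |

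Both lead to the other drug's rules. A hematologic example shows that the 5.4.4 error changes the action. For a first Grade 4 thrombocytopenia, Table 2 withholds until platelets exceed 25,000/µL without Grade 2 or higher bleeding and allows restart at the original dose. Table 4 interrupts for the remainder of the cycle and then reduces by one level.

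**Step 4: size.** SAP section 1 reports 11 subjects treated in Phase 1, and SAP section 6 states that Phase 2 was not initiated. Neither document gives a rate for manageable Grade 4 non-hematologic events, so 11 is a ceiling and no affected count is estimated.

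**The case against.** The strongest defence is that the two sections add to each other. Section 5.4.3 never says that ibrutinib is held only for unmanageable events. It applies the 5.4.4 criteria at each cycle start, cites 5.4.4 in the hold sentence itself, and sends other clinically important events to the Medical Monitor. Section 5.4.4 is a free-standing instruction with its own withhold action, so a site that follows both sections faces no conflict. Manageable Grade 4 events attributed to ibrutinib should also be uncommon. On the pointers, Tables 2 and 3 sit directly below the misdirected sentence, and Table 4 names pomalidomide and 1 mg steps, so a site would probably notice.

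Most of this stands. It rules out reading 5.4.3 and 5.4.4 as opposite commands, and it confines the gap to mid-cycle. It does not remove the gap: the hold sentence refers hematologic toxicity to 5.4.4 but states its own, narrower non-hematologic rule. Nor does it make the pointers right.

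A reader might also infer that the pomalidomide rules conflict. Section 5.5.5 states "Treatment with pomalidomide should be withheld for any potentially study drug-related non-hematological toxicity that is Grade 3 or higher in severity", while the residual row of Table 4 covers "Any other Grade 3/4 non-hematologic toxicities attributed to pomalidomide". The documents do not support calling this an error:

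- The term study drug is not used uniformly. Section 3 applies it to ibrutinib or matching placebo, and 7.6.1 to all three agents. If 5.5.5 means pomalidomide alone, the supposed difference in which drug counts disappears.
- On the wider reading, holding on suspicion and reducing on attribution is a coherent scheme, and a defensible one where Protocol 1.4 acknowledges a lack of safety data for the combination.
- The restart dose is not left open. After an in-cycle hold, 5.5.5 resumes treatment "provided the subject meets the cycle initiation criteria above, with dose adjustments as per Table 4", and it says that a delayed Day 1 start is made without dose modification. Where no row of Table 4 applies, the natural reading is the same dose.

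**Conclusion.** The point holds in a narrow form. For mid-cycle non-hematologic toxicity, the 5.4.3 hold sentence is silent on manageable Grade 4 events that 5.4.4 and Table 2 withhold for, and two pointers name the wrong rules. The threshold finding rests on two readings: that unmanageable in the 5.4.4 residual trigger modifies Grade 3 only, which is its plain grammar, and that Table 2 is the intended action table, which its title and position support. The pointer errors need no interpretation.

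The practical reach is at most 11 subjects. A reader might infer an effect on DLT counts or the MTD. The documents do not support that: 5.1.1 already counts a Grade 3 or higher non-hematologic event as a DLT when a relationship to study drug cannot be ruled out, whether or not the dose is held. No effect on power or on SAP outputs is claimed either. The correction is still worth making, because literal compliance gives the wrong dosing rule and the edits cost almost nothing.

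**What to change.** Make three wording edits:

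1. In the 5.4.3 hold sentence, withhold for *any non-hematologic or hematologic toxicity meeting the criteria in Section 5.4.4*, which for the residual category means Grade 4 or unmanageable Grade 3.
2. In 5.4.4, change the reference from Table 4 to Table 2.
3. In 5.5.4, change the reference from 5.4.5 to 5.5.5 and 5.5.6.

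The first edit also takes its attribution test from 5.4.4. If the sponsor wants to keep holding for unmanageable events that are only suspected to be related, the present clause should stay alongside the new one.

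Leave the pomalidomide attribution wording in 5.5.5 and Table 4 alone. Extending the residual row to every event whose relationship cannot be ruled out would force a 1 mg reduction for events of uncertain cause. At most, add a line saying that a pomalidomide hold with no matching Table 4 row resumes at the same dose.

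The cost is slightly more mid-cycle ibrutinib holds at sites that had relied on 5.4.3 alone. Data collection and analysis do not change.

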5.4.4. Dose Modification of Ibrutinib or Placebo

The dose of ibrutinib or placebo should be modified according to the dose modification guidelines in Table 4 if any of the following toxicities occur:

- Grade 4 neutropenia (ANC <500/ μ L) for more than 7 days. Refer to Section 6 for instruction regarding the use of growth factor support
- Grade 3 thrombocytopenia (platelets <50,000/ μ L) in the presence of clinically significant bleeding events
- Grade 4 thrombocytopenia (platelets <25,000/ μ L)
- Grade 3 or 4 nausea, vomiting, or diarrhea if persistent, despite optimal anti-emetic and/or anti-diarrheal therapy
- Any other Grade 4 or unmanageable Grade 3 toxicity attributed to ibrutinib or placebo

For Grade 3 or 4 atrial fibrillation or persistent atrial fibrillation of any grade, consider the risks and benefits of ibrutinib or placebo treatment.

If clinically indicated, the use of anticoagulants or antiplatelet agents may be considered for the thromboprophylaxis of atrial fibrillation (Section 6.1.2.4).

Table 2: Ibrutinib or Placebo Dose Modification Guidance

Hematologic Adverse Events	
Occurrence	Action to be Taken
First	Withhold ibrutinib or placebo until recovery to an ANC $\geq 750 \mu\text{L}$ or platelets $> 25,000 \mu\text{L}$ with no evidence of Grade ≥ 2 bleeding; may restart at original dose level
Subsequent ^a	Withhold ibrutinib or placebo until recovery to an ANC $\geq 750 \mu\text{L}$ or platelets $> 25,000 \mu\text{L}$ with no evidence of Grade ≥ 2 bleeding; may restart at 1 dose level lower (refer to Table 3)
Non-Hematologic Adverse Events	
Occurrence	Action to be Taken
First	Withhold ibrutinib or placebo until recovery to Grade ≤ 1 or baseline; may restart at original dose level
Subsequent ^a	Withhold ibrutinib or placebo until recovery to Grade ≤ 1 or baseline; may restart at 1 dose level lower (refer to Table 3)

^a Do not dose below 280 mg daily

Table 3: Ibrutinib or Placebo Dose Modifications

Starting Dose Level	840 mg	560 mg	420 mg
Dose Reduction Level 1	700 mg	420 mg	280 mg
Dose Reduction Level 2	560 mg	280 mg	140 mg
Dose Reduction Level 3	420 mg	Discontinue	Discontinue
Dose Reduction Level 4	280 mg	NA	NA
Dose Reduction Level 5	Discontinue	NA	NA

For required dose modification for hepatic impairment refer to Section 5.4.5 and for concomitant treatment with CYP3A inhibitors refer to [Section 6.1.2.1](#).

If ibrutinib or placebo is discontinued for toxicity, subject will end the Treatment Phase of the study.

